9.5. Missed Evaluations

Evaluations should occur within the visit window specified by the protocol. If an evaluation is missed, reschedule and perform it as close as possible to the original date. If rescheduling becomes, in the investigator's opinion, medically unnecessary because the evaluation would occur too close to the next scheduled evaluation, it may be omitted.

10. EVALUATION, RECORDING, AND REPORTING OF ADVERSE EVENTS

10.1. Definitions

10.1.1. Adverse Event (AE)

An AE is any untoward medical occurrence associated with the use of a drug in humans, whether or not considered drug related. An AE can therefore be any unfavorable and unintended sign (including a clinically significant abnormal finding in laboratory tests or other diagnostic procedures), symptom, or disease temporally associated with the use of a drug, without any judgment about causality. An AE can arise from any use of the drug and from any route of administration, formulation, or dose, including an overdose.

Disease progression is not considered to be an AE or SAE. If there are specific AEs that are always part of disease progression, these do not need to be reported as AEs or SAEs. Pre-existing medical conditions (other than natural progression of the disease being studied) judged by the investigator or subject to have worsened in severity or frequency or changed in character during the protocol-specified AE reporting period will be reported as AEs or SAEs as appropriate.

An AE or SAE can also be a complication that occurs as a result of protocol mandated procedures (eg, invasive procedures such as biopsies).

10.1.2. Serious Adverse Events (SAEs)

An AE is considered serious, if in the view of either the investigator or sponsor, it results in any of the following outcomes:

- Death.
- A life-threatening AE.

An AE is considered "life-threatening" if in the view of either the investigator, or sponsor, its occurrence places the subject at immediate risk of death. It does not include an AE that, had it occurred in a more severe form, might have caused death.

- Inpatient hospitalization or prolongation of an existing hospitalization.
- A persistent or significant incapacity or substantial disruption of the ability to conduct normal life functions.
- A congenital anomaly or birth defect.

Important medical events that may not result in death, be life-threatening or require hospitalization may be considered serious when, based on the appropriate medical judgment, they may jeopardize the subject and may require medical or surgical intervention to prevent one of the outcomes listed in the definition of SAE. Examples of such medical events are intensive treatment in an emergency room or at home; blood dyscrasias or convulsions that do not result in inpatient hospitalization; or development of drug dependency or drug abuse.

10.2. Adverse Event Reporting and Descriptions

Record new AEs from the start of study treatment until 30 days after the last dose of study treatment or until the subject starts new anticancer treatment, including new investigational treatment, whichever occurs first. Also record screening procedure-related AEs that occur before the start of study treatment. Collection of AEs may also continue until the decision is made to permanently discontinue study treatment.

Record all AEs either observed by the investigator or one of the medical collaborators, or reported by the subject spontaneously, or in response to the direct question below, in the AEs section of the subject's eCRF, in the source document, and if applicable, record on the SAE Report form. Whenever possible, the investigator should group signs and symptoms (including laboratory tests or other results of diagnostic procedures) into a single diagnosis under a single term. For example, cough, rhinitis, and sneezing might be reported as "upper respiratory infection" or a pulmonary infiltrate, positive sputum culture and fever might be reported as "pneumonia."

To optimize consistency of AE reporting across centers, ask the subject a standard, general, non-leading question to elicit any AEs (such as "Have you had any new symptoms, injuries, illnesses since your last visit?").

Death is an outcome of an SAE and usually not itself an SAE, unless it is death with no identifiable cause or event. In all other cases, record the cause of death as the SAE. Investigators will assess the status of previously reported, and occurrence of new AEs and SAEs at all subject evaluation time points during the study.

10.2.1. Severity

Use the definitions found in the CTCAE v4.03 for grading the severity (intensity) of AEs. The CTCAE v4.03 displays Grades 1 through 5 with unique clinical descriptions of severity for each referenced AE and provides guidance not listed. Should a subject experience any AE not listed in the CTCAE v4.03, use the following grading system to assess severity:

- Grade 1 Mild; asymptomatic or mild symptoms; clinical or diagnostic observations only; intervention not indicated.
- Grade 2 Moderate; minimal, local or noninvasive intervention indicated; limiting age-appropriate instrumental activities of daily living (ADL), such as preparing meals, shopping for groceries or clothes, using the telephone, managing money, etc.
- Grade 3 Severe or medically significant but not immediately life-threatening; hospitalization or prolongation of hospitalization indicated; disabling; limiting selfcare ADL, such as bathing, dressing and undressing, feeding self, using the toilet, taking medications, and not bedridden.
- Grade 4 Life-threatening consequences; urgent intervention indicated.
- Grade 5 Death related to AE.

10.2.2. Relationship to Study Treatment (Suspected Adverse Reactions)

Assess all AEs/SAEs for relationship to study treatment or if applicable, to study procedure.

If an AE/SAE occurs before the first dose of study treatment, report it only if it is considered related to a study-specific procedure (eg, bleeding or local infection after skin punch biopsy). Those events will be recorded in the study database but will not be part of the treatment-emergent AE analysis.

To ensure consistency of AE and SAE causality assessments, investigators should apply the general guideline shown below.

Related (Suspected Adverse Reaction)	A suspected adverse reaction means any AE for which there is a reasonable possibility that the drug caused the AE. Reasonable possibility means there is evidence to suggest a causal relationship between the drug and the AE such as a plausible temporal relationship between the onset of the AE and administration of the drug; and/or the AE follows a known pattern of response to the drug; and/or the AE abates or resolves upon discontinuation of the drug or dose reduction and, if applicable, reappears upon rechallenge. Further examples of type of evidence that would suggest a causal relationship between the drug and the AE:
	• A single occurrence of an event that is uncommon and known to be strongly associated with drug exposure (eg, angioedema, hepatic injury, Stevens-Johnson Syndrome),
	• One or more occurrences of an event that is not commonly associated with drug exposure, but is otherwise uncommon in the population exposed to the drug (eg, acute myocardial infarction in a young woman),
	• An aggregate analysis of specific events observed in a clinical study (such as known consequences of the underlying disease or condition under investigation or other events that commonly occur in the study population independent of drug therapy) that indicates those events occur more frequently in the drug treatment group than in a concurrent or historical control group.
Not Related	Adverse events that do not meet the definition above.

Not Related (Not Suspected)

10.2.3. Reporting Requirements for Pregnancy and Abortion

Report any pregnancy that occurs in a subject or male subject's female partner during the time between the first study-specific procedure and 90 days after the last dose of study treatment. Record any occurrence of pregnancy on the Pregnancy Report Form Part I and email it to the Sponsor's Pharmacovigilance group or designee within 24 hours of learning of the event. After the birth of the baby, collect and report additional information on the baby until the baby is 1 year old by completing the Pregnancy Report Form Part II.

Sponsor's Pharmacovigilance Group Contact Information					
PRIMARY CONTACT: email	[contact]				

A subject must immediately inform the investigator if the subject or subject's partner becomes pregnant during the time between the first study-specific procedure and 90 days after the last dose of study treatment. Any female subjects receiving ASTX029 who become pregnant must immediately discontinue study treatment. The investigator should counsel the subject, discussing any risks of continuing the pregnancy and any possible effects on the fetus.

Report any abortion and the reason for it, whether therapeutic, elective or spontaneous, to the Sponsor's Pharmacovigilance group or designee within 24 hours of learning of the event, through the SAE reporting process (Section 10.2.4).

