Note: Other gene aberrations that in the investigator's opinion may confer sensitivity to ASTX029 may be included in Cohort F after obtaining approval from the Sponsor's medical monitor.

For each potential subject, there is an up to 21-day screening and eligibility assessment period before enrollment; the first dose of study treatment will be administered on Cycle 1 Day 1 (C1D1). Subjects will continue to receive their assigned treatments throughout the study until the occurrence of disease progression, death, or unacceptable treatment-related toxicity; they elect to discontinue study treatment or withdraw consent to continue study participation; or until the study is closed by the sponsor.

Study visits will take place weekly during Cycles 1 and 2 and less frequently thereafter (see Table 11 and Table 12 for the complete schedules of events for the Regimen 1 and Regimen 2, respectively). Serial blood samples will be collected for PK and biomarker analyses at specified time points. If a formalin-fixed paraffin-embedded (FFPE) archived tumor biopsy is available, it will be obtained for use in this study during screening. In addition, in Phase 1 Part A and Phase 2, fresh tumor biopsies are optional during screening and posttreatment during Cycle 2. In

Phase 1 Part B, fresh tumor biopsies are mandatory during screening and posttreatment during Cycle 2.

Upon permanent discontinuation of study treatment, there is a Treatment Termination (Tx Term) visit and a 30-day (± 5 days or within 3 days before starting new treatment) Safety Follow-up visit. Subjects who remain on study after the 30-day Safety Follow-up visit will be contacted periodically by telephone for collection of long-term health status information.

Tolerability and safety of study treatment will be evaluated throughout the study by collection of clinical and laboratory data. Antitumor response will be assessed according to standard Response Evaluation Criteria in Solid Tumors (RECIST) v1.1 using computed tomography (CT) or magnetic resonance imaging (MRI) scans. Subjects whose disease is not measurable using RECIST v1.1 will be evaluated using another appropriate method.

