5.2. Inclusion Criteria

To be eligible for the study, subjects must fulfill all of the following inclusion criteria:

- 1. Able to understand and comply with the study procedures, understand the risks involved in the study, and provide written informed consent before any study-specific procedure is performed.
- 2. Men or women 18 years of age or older.
- 3. Subjects with histologically or cytologically confirmed advanced solid tumors that are metastatic or unresectable, who are refractory or have relapsed after treatment with available therapies or for whom standard life-prolonging measures or approved therapies are not available. In Phase 1 Part B and in the Phase 2 portion of the protocol, subjects must also have documented gene alterations in the MAPK pathway as detailed in Section 4.1.1, Section 4.1.2, and Table 2.
- 4. In Phase 1 Part B of the protocol, subjects must have disease lesions that are amenable to biopsy.
- 5. In the Phase 2 portion of the protocol, subjects must have measurable disease according to Response Evaluation Criteria in Solid Tumors (RECIST) v1.1.
- 6. Eastern Cooperative Oncology Group performance status 0 to 2.
- 7. Acceptable organ function, as evidenced by the following laboratory data:
 - a. AST and alanine aminotransferase (ALT) $\leq 2 \times$ upper limit of normal (ULN) or ≤ 3 ULN in the presence of liver metastases.
 - b. Total serum bilirubin $\leq 1.5 \times ULN$.
 - c. Absolute neutrophil count (ANC) \geq 1500 cells/mm³.
 - d. Platelet count $\geq 100,000$ cells/mm³.
 - e. Calculated creatinine clearance (by the standard Cockcroft-Gault formula) of $\geq 50 \text{ mL/min}$ or glomerular filtration rate of $\geq 50 \text{ mL/min}$.

- 8. Women of child-bearing potential (according to recommendations of the Clinical Trial Facilitation Group [CTFG]; see below* for details) must not be pregnant or breastfeeding and must have a negative pregnancy test (urine or serum as required by local regulations) within 24 hours before the first dose of study treatment. Women of child-bearing potential must agree to the following during the treatment period and for at least 32 days (approximately 5 half-lives of ASTX029 or metabolite plus 30 days) after receipt of last dose of study treatment:
 - a. Refrain from donating eggs (ova, oocytes) for the purpose of reproduction.

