 - b. Use a contraceptive method** that is highly effective with a failure rate of <1% per year), with low user dependency. The investigator should evaluate the effectiveness of the contraceptive method before the first dose of study treatment. The investigator is responsible for review of medical history, menstrual history, and recent sexual activity to decrease the risk for inclusion of a woman with an early undetected pregnancy.
- 9. Men with a pregnant partner or non-pregnant partner who is a woman of childbearing potential must agree to the following during the treatment period and for at least 92 days (approximately 5 half-lives of ASTX029 or metabolite plus 90 days) after receipt of last dose of study treatment:
 - a. Refrain from donating sperm.
 - b. Be abstinent from heterosexual intercourse as their preferred and usual lifestyle (abstinent on a long term and persistent basis) and to remain abstinent OR to use a male condom when having sexual intercourse with a woman of childbearing potential (according to recommendations of the CTFG; see below* for details) who is not currently pregnant, and the female partner should be advised of the benefit of using an additional highly effective contraceptive method** with a failure rate of <1% per year as a condom may break or leak. The investigator should evaluate the effectiveness of the contraceptive method before the first dose of study treatment.

*According to recommendations of the CTFG (http://www.hma.eu /fileadmin/dateien /Human_Medicines/01-About_HMA/Working_Groups/CTFG/2020_09_HMA_ CTFG_Contraception_guidance_Version_1.1_updated.pdf), a woman is considered of childbearing potential (ie, fertile) following menarche and until becoming postmenopausal, unless permanently sterile. Permanent sterilization methods include hysterectomy, bilateral salpingectomy, and bilateral oophorectomy. A man is considered fertile after puberty unless permanently sterile by bilateral orchidectomy.

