9.3.1. Adverse Events

The AEs should be captured from the time of first dose until 30 days after the last dose of study treatment or the start of an alternative treatment, whichever occurs first. The AEs that occur during the screening period and are considered related to screening procedures, as well as all related SAEs occurring beyond 30 days from the last dose of study treatment, will also be captured. Any SAEs will be followed until they have resolved or are stable.

The following events will be recorded in the eCRF as AEs:

- Adverse events of any severity grade (including changes from screening).
- Clinically significant abnormal findings during clinical assessments, including PEs and vital signs.
- Clinically significant abnormal ECG readings and any clinically significant ECHO/MUGA results.
- Spontaneous subject reports.
- Baseline medical conditions and AEs, other than the primary disease under evaluation, that worsen in severity or frequency during the study.

Clinical hematology, coagulation, serum chemistry, and urinalysis results that are outside of normal ranges but are not considered by the investigator to be clinically significant will not be reported as AEs.

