Response assessment ^w	х	At th	At the end of every 2 cycles (±7 days) for the first 4 cycles and then every 4 cycles (±1 cycle) thereafter										
Health status follow-up ^x					-								Every 3 months

AE=adverse event; CxDx=Cycle x Day x; CBC=complete blood count; ctDNA=circulating tumor DNA; CT=computed tomography; ECG=electrocardiogram; ECOG=Eastern Cooperative Oncology Group; eCRF=electronic case report form; FFPE=formalin-fixed paraffin embedded; FU=follow-up; INR=international normalized ratio; MRI=magnetic resonance imaging; MUGA=multiple-gated acquisition; PBMC=peripheral blood mononuclear cell; PE=physical examination; PK=pharmacokinetic; PTT= partial thromboplastin time; Tx Term=Treatment Termination.

^a After Cycle 6, the specific visit schedule and assessments are at the investigator's discretion; at a minimum, information should be collected regarding concomitant medications, AEs, dosing compliance, and, at least once a month, pregnancy tests. Continue to collect efficacy and response assessments, in the manner described in the protocol, until disease progression (for response assessment) or death (for survival assessment), or the subject withdraws consent.

^b Perform Tx Term visit procedures when a subject permanently discontinues study treatment, regardless of whether or not the subject plans to continue participating in the study (unless consent to continue study participation is withdrawn by the subject). The visit is to occur within 7 days after the last study treatment or within 3 days before starting new anticancer treatment and before the 30-day Safety Follow-up visit. If a subject discontinues study treatment at a scheduled visit, the assessments at that visit can be used to fulfill the Tx Term visit requirements.

^c The 30-day Safety Follow-up visit must occur 30 (+5) days after the last dose of ASTX029 or within 3 days before starting new cancer treatment.

^d In Phase 1 starting with C2D8, study visits have a visit window of ± 1 day. In Phase 2, all study visits for Cycles ≥ 2 have a visit window of ± 2 days.

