9.4.15. Long-Term Follow-up of Health Status

For subjects who remain on study, beginning 3 months after the discontinuation of study treatment, the subject's health status will be collected by telephone every 3 months until death, or the subject withdraws consent, or until the end of the study, whichever occurs first. The following health information will be collected and recorded in the source documents and eCRF:

- Survival information.
- Date of disease progression if subject did not have disease progression at the time they discontinued study treatment.

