10.2.4. Reporting Requirements for Serious Adverse Events (SAEs)

All SAEs regardless of causality will be reported by the investigator to the Sponsor through the 30-day period after the last dose of study treatment. Deaths and SAEs occurring after the 30-day safety follow-up period AND considered related to study treatment or study procedures must also be reported until the end of the study or subject death.

Report all SAEs (initial and follow-up information) on the SAE Report form and email it to the Sponsor's Pharmacovigilance group or designee, within 24 hours of learning of the event or information (see below). The Sponsor may request follow-up and other additional information from the investigator (eg, hospital admission or discharge notes, laboratory results).

Sponsor's Pharmacovigilance Group Contact Information					
PRIMARY CONTACT: email	[contact]				

Report all deaths with the primary cause of death as the SAE term, as death is the outcome of the event, not the event itself. If an autopsy was performed, report the primary cause of death on the autopsy report as the SAE term. Forward autopsy and postmortem reports to the Sponsor's Pharmacovigilance group or designee, as outlined above.

If study treatment is discontinued, temporarily suspended, or dose reduced because of an SAE, include this information in the SAE Report form.

Suspected Unexpected Serious Adverse Reactions (SUSARs) are SAEs that qualify for mandatory expedited safety reporting to regulatory authorities where the SAE is suspected to be caused by the study treatment and is considered unexpected (ie, not listed as expected in the Reference Safety Information section of the current IB, clinical study protocol, or approved

labeling for marketed drugs). In this case, the Sponsor's Pharmacovigilance group or designee will report to the relevant regulatory authorities and forward a formal notification describing the SUSAR to investigators, according to regulatory requirements. Each investigator must then notify his or her IRB/IEC of the SUSAR as required by local regulatory authorities and in accordance with IRB/IEC policy.

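### Three post-treatment safety rules do not match the protocol's own windows: partner-pregnancy reporting (90 against 92 days), the 30-day visit (±5 against +5 days), and no prompt for late related SAEs at the 3-monthly calls

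*Protocol*

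**What the plan says.** **Pregnancy.** Protocol Section 10.2.3 covers a pregnancy in a subject or a male subject's partner "during the time between the first study-specific procedure and 90 days after the last dose of study treatment". The same limit appears twice: once for the investigator's report and once for the subject's duty to tell the investigator. The report is due within 24 hours of the site learning of the pregnancy. In Section 5.2, criterion 9 binds men "for at least 92 days (approximately 5 half-lives of ASTX029 or metabolite plus 90 days) after receipt of last dose of study treatment", and criterion 8 binds women "for at least 32 days (approximately 5 half-lives of ASTX029 or metabolite plus 30 days) after receipt of last dose of study treatment".

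**30-day visit.** Section 4.1.2 provides for "a 30-day (± 5 days or within 3 days before starting new treatment) Safety Follow-up visit", and Section 9.4.14 repeats the ±5 days. Footnote c of Tables 11 and 12 (Section 9.4.9) says instead: "The 30-day Safety Follow-up visit must occur 30 (+5) days after the last dose of ASTX029". Table 13, for the extension phase, also allows only +5. On the collection period, Section 9.3.1 says: "The AEs should be captured from the time of first dose until 30 days after the last dose of study treatment", or until alternative treatment starts if that is sooner. Section 5.4.1 makes day 30 the minimum end of safety follow-up.

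**After the 30-day visit.** Section 10.2.4 says: "Deaths and SAEs occurring after the 30-day safety follow-up period AND considered related to study treatment or study procedures must also be reported", up to the end of the study or the subject's death. Section 9.3.1 also keeps related SAEs open beyond day 30, and SAP Section 7.6.2 counts serious related events from that period as treatment-emergent. Long-term follow-up is a telephone call every 3 months. Section 9.4.15 introduces its content with "The following health information will be collected and recorded in the source documents and eCRF" and then lists two items: survival, and the progression date for those not already progressed. In Tables 11 and 12 the AE row stops at the 30-day visit, and the long-term column carries only health status.

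**The concern.** The protocol states how long exposure is treated as a risk and how long safety data are to be collected. The operating rules should cover those periods. In one place a reporting rule ends before the risk period does. In another, two binding statements about the same visit disagree, and one of them leaves part of the collection period without a contact. In the third, a duty to report has no matching question at the scheduled call.

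The stakes are ascertainment. This is a first-in-human study, and Section 7.3 gives weight to late or cumulative toxicity when doses are recommended. A late related SAE that nobody asks about can only be missed; lack of a prompt cannot add events. Any error in the SAP's treatment-emergent count from this source is therefore downward. For pregnancy, an exposure inside the protocol's stated risk period could fall outside the duty to inform pharmacovigilance.

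**Working it through.** This is day arithmetic, counted from the last dose. No sample size, power or alpha is involved.

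**Inputs**

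| Rule | Days | Source |
|---|---|---|
| Pregnancy reporting, both sexes | to 90 | Protocol 10.2.3 |
| Contraception, men | 92 | Protocol 5.2, criterion 9 |
| Contraception, women | 32 | Protocol 5.2, criterion 8 |
| 30-day visit, text | 30 ±5 | Protocol 4.1.2, 9.4.14 |
| 30-day visit, tables | 30 (+5) | Tables 11, 12, 13 |
| AE collection | to 30 | Protocol 9.3.1 |
| First call | 3 months | Protocol 9.4.15 |

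**Check on the stated 92 days.** The documents give no human half-life, so 92 cannot be derived independently. The two windows do agree with each other: women, 32 − 30 = 2 days for 5 half-lives; men, 2 + 90 = 92 days.

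**1. Pregnancy: reporting limit minus contraception window**
- Men's partners: 90 − 92 = −2 days, a gap covering days 91 and 92 (2/92 = 2.2% of the window).
- Women: 90 − 32 = +58 days, no gap.

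**2. 30-day visit**
- Text: earliest 30 − 5 = day 25, latest 30 + 5 = day 35. AE-collection days left after the earliest visit: 30 − 25 = 5, and 5/30 = 17%.
- Tables: earliest day 30, latest day 35. Days left after the earliest visit: 30 − 30 = 0.

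The separate rule for subjects starting new cancer treatment is set aside here; it appears in both the text and Tables 11 and 12.

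**3. Calls.** Taking discontinuation as the last dose, and 30.4375 days per month (the divisor in SAP Section 7.6.1), the first call falls at 3 × 30.4375 = day 91.3. That is 91.3 − 25 = 66 days after the earliest 30-day visit the text allows, and 91.3 − 35 = 56 days after the latest. The procedure list for the 30-day visit in Section 9.4.14 includes AEs but no pregnancy item. The call list in Section 9.4.15 has neither an SAE nor a pregnancy item.

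**Can one pregnancy question, at the first call, be enough?** Assume recognition 4 to 6 weeks after conception; the documents give no figure. A conception on day 92 is then recognised between 92 + 28 = day 120 and 92 + 42 = day 134. That is after the first call (day 91) and before the second (2 × 91.3 = day 183). The question therefore has to be asked at more than the first call.

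**The case against.** The strongest defence has four parts.

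- **Pregnancy reporting turns on when the pregnancy occurs.** Section 10.2.3 sets no last date for learning of it, only a 24-hour clock once it is known, and it obliges the subject to inform the investigator without waiting for a call. This stands. A reader might infer that, because recognition lags conception by weeks, a large part of the 92 days is lost. The wording does not support that: a conception on day 60 discovered on day 100 is still reportable. The gap is the 2 days.
- **An early visit does not shorten AE collection.** This stands. Sections 9.3.1 and 10.2 run to day 30 (or new anticancer treatment) whatever the visit date. A reader might infer that collection closes at day 25; it does not. What is missing is a scheduled contact.
- **Late SAEs are already covered.** Related SAEs stay reportable to the end of the study. Section 10.2 has investigators assess for new SAEs at every evaluation time point and supplies a standard open question. SAEs go on their own form, so Section 9.4.15 need not list them, and the survival item will reveal deaths. This stands in part. It rules out any claim that collection closes. But neither Section 9.4.15 nor the long-term column of Tables 11 and 12 carries the Section 10.2 instruction into the calls, so a site following the schedule would not ask.
- **The 30-day window is generous.** The implied 5 half-lives is about 2 days, so the window extends 30 − 2 = 28 days further. This stands; nothing here says the AE window is too short.

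**Conclusion.** The point holds in limited form: two rules conflict with the protocol's own figures, and one reporting duty has no matching prompt at the scheduled call.

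- Partner pregnancies on days 91 and 92 fall inside the stated risk period and outside both duties in Section 10.2.3. This is exact and affects male subjects' partners only.
- The text and the tables give incompatible windows for the 30-day visit. Under the text, up to 5 of 30 AE-collection days can pass without a scheduled contact. Only the tables' wording is consistent with Section 5.4.1.
- Late related SAEs are reportable and enter the SAP's treatment-emergent count, but the long-term calls do not ask about them.

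A reader might go further and conclude that the late SAE count is materially biased. The documents give no rate of late related SAEs, so the direction of any error can be stated but its size cannot. The day counts rest on the documents alone. The date of the first call assumes that discontinuation is the last dose, and the case for repeating the pregnancy question uses the assumed 4 to 6 week lag.

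**What to change.** 1. **Sections 10.2.3 and 5.2.** Reconcile them so that reporting, and the subject's duty to inform, for partners of male subjects does not end before the male contraception window. Leave the 90-day reporting for female subjects as it is. Tying reporting to the Section 5.2 window for everyone would cut women's reporting from day 90 to day 32.
2. **Sections 4.1.2 and 9.4.14 against Tables 11 to 13.** Reconcile the visit window, checking the result against the day-30 minimum in Section 5.4.1.
3. **Section 9.4.15 and the long-term column of Tables 11 and 12.** Add two questions to the existing calls: any SAE since the last contact, for the investigator to assess for relatedness; and any pregnancy in the subject or partner that occurred during the reporting period, asked at more than the first call.

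The cost is some wording changes and two more items on an existing call form, with slightly less flexibility in scheduling the visit if the tables' window is kept. No new visit or test is needed.
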